7.1.4. Pharmacokinetic Assessments

Blood and urine samples will be collected to assess concentrations of VIR-2218 and metabolites, as applicable. Detailed schedules of timepoints for the collection of samples for VIR-2218 PK analysis for Part A of the study are provided in Appendix 4. Timepoints for the collection of samples for VIR-2218 PK analysis for Part B/C of the study are provided in Appendix 5.

Details regarding the processing, shipping, and analysis of the samples are provided in the Laboratory Manual.

CCI

7.2. Safety Assessments

The assessment of safety during the study will consist of the surveillance and recording of AEs including SAEs, recording of concomitant medications, physical examination findings, alcohol assessment, ECG, and laboratory tests. All AEs related to screening activities must be collected from the time of consent onwards; any other events occurring during the screening period should be reported as medical history. All SAEs must be collected from the time of consent onwards.

7.2.1. Physical Examination

A full physical examination will include general appearance, head, neck, chest/respiratory, heart/cardiovascular, gastrointestinal/liver, extremities, skin, and screening neurological assessments.

A symptom-directed physical examination will be performed according to investigator discretion.

7.2.2. Alcohol Assessment

Alcohol intake during the study will be recorded.

7.2.3. Height and Weight

Height and body weight will be measured. Body mass index will be calculated from height and weight.

7.2.4. Vital Signs

Vital sign measurements include blood pressure, pulse rate, temperature (oral preferred), and respiratory rate. Vital signs should be measured after the subject has rested comfortably for approximately 10 minutes. When scheduled at the same timepoints, the assessments of vital signs and 12-lead ECGs must be performed first, before the physical examinations, blood sample collections, and urine collections.

7.2.5. Electrocardiogram

Safety ECGs: 12-lead safety ECGs will be recorded and reviewed on-site by the investigator as outlined in Appendix 2 and Appendix 3. Specified collection timepoints for each visit are provided in Appendix 4 and Appendix 5.

Cardiodynamic ECG evaluation (Part A only): (12-lead ECGs extracted from continuous Holter recordings): Up to 10 replicate ECGs may be extracted by the central ECG core laboratory at

timepoints provided in Appendix 4 and Appendix 5. Subjects will be resting supine for at least 10 minutes prior to and 5 minutes after each nominal time point. 12-lead ECGs will be extracted from the 5-minute time window following the nominal time point. When scheduled at the same time points, the assessments of vital signs and 12-lead ECGs should be performed first, before the physical examinations, blood sample collections, and urine collections.

In Part A, the 12-lead Holter and ECG equipment will be supplied and supported by the central ECG core laboratory. All cardiodynamic ECG data will be collected using a Global Instrumentation M12R ECG continuous 12-lead digital recorder. The continuous 12-lead digital ECG data will be stored onto SD memory cards. ECGs to be used in the analyses may be selected by pre-determined time points as defined in Appendix 4 and Appendix 5, and cardiodynamic ECGs will be stored and may be read by the central ECG core laboratory.

The following principles will be followed in the central ECG core laboratory:

- ECG analysts are blinded to the subject, visit, and treatment allocation
- Baseline and on-treatment ECGs for a particular subject will be over-read on the same lead and will be analyzed by the same reader
- The primary analysis lead is lead II. If lead II is not analyzable, then primary lead of analysis will be changed to another lead for the entire subject data set.

The following is a brief description of ECG analysis methods utilized by the central ECG core laboratory.

TQT Plus ECG Extraction Technique

Ten 14-second digital 12-lead ECG tracings may be extracted from the continuous Holter recordings using the ‘TQT Plus method’, a computer-assisted and statistical process utilized by the central ECG core laboratory. The method enables extraction of ECGs with the lowest HR variability and noise within the protocol-specified extraction time window (eg, the HR and QT changes from beat-to-beat in the range of < 10%). At each protocol-specified timepoint, 10 ECG replicates may be extracted from a 5-minute “ECG window” (typically, the last 5 minutes of the 15-minute period when the subject is maintained in a supine or semi-recumbent quiet position).

Expert-Precision QT Analysis

Expert-precision QT analysis may be performed on all analyzable (non-artifact) beats in the 10 ECG replicates. Statistical quality control procedures are used to review and assess all beats and identify “high” and “low” confidence beats using several criteria, including:

- QT or QTc values exceeding or below certain thresholds (biologically unlikely).
- RR values exceeding or below certain thresholds (biologically unlikely).
- Rapid changes in QT, QTc or RR from beat to beat.

Measurements of all primary ECG parameters (QT, QTc, RR) in all recorded beats of all replicates that are deemed “high confidence” are performed using COMPAS software. All low-confidence beats are reviewed manually and adjudicated using pass-fail criteria. The final QC assessment is performed by a cardiologist. The beats found acceptable by manual review are included in the analysis. The median QT, QTc, and RR value from each extracted replicate is calculated, and then the mean of all available medians from a nominal timepoint is used as the subject’s reportable value at that timepoint.

T-wave morphology categories are presented in Table 5. Categorical T-wave morphology analysis and the measurement of PR and QRS intervals will be performed manually in 3 of the 10 ECG replicates at each timepoint. Each fiducial point (onset of P-wave, onset of Q-wave, offset of S-wave, and offset of T-wave) is electronically marked.

In addition to the T-wave categorical analysis, the presence of abnormal U-waves is noted.

Table 5. T-Wave Morphology Categories (Assessed Manually)

Category	Description
Normal T-wave	Any T-wave not meeting any criterion below
Flat T-waves	T amplitude < 1 mm (either positive or negative) including flat isoelectric line
Notched T-wave (+)	Presence of notch(es) of at least 0.05 mV amplitude on ascending or descending arm of the positive T-wave
Biphasic	T-wave that contains a second component with an opposite phase that is at least 0.1 mV deep (both positive and negative/positive and polyphasic T-waves included)
Normal T-wave (-)	T amplitude that is negative, without biphasic T-wave or notches
Notched T-wave (-)	Presence of notch(es) of at least 0.05 mV amplitude on descending or ascending arm of the negative T-wave

7.2.6. Pregnancy Testing

A pregnancy test or confirmation of post-menopausal status must be confirmed for all female subjects. Post-menopausal status is defined as age > 50 years with no menses for at least 2 years at the time of screening. Pregnancy tests will be performed for WOCBP only. Pregnancy testing will be performed per the schedule of assessments (SoA) and any time pregnancy is suspected. A WOCBP who is known to be pregnant or who does not have a negative pregnancy test at screening is not eligible for study participation. A serum pregnancy test will be performed at screening and urine pregnancy tests will be performed thereafter. During the study, the results of these pregnancy tests must be known prior to study drug administration. A WOCBP determined to be pregnant while on study will be followed until the pregnancy outcome is known, as described in Section 8.5.2.

7.2.7. Clinical Laboratory Assessments

Clinical laboratory tests that will be performed in this study are presented in Table 6. In the event of an unexplained clinically relevant abnormal laboratory test occurring after study drug administration, the test should be repeated and followed up at the discretion of the investigator until it has returned to the normal range or stabilized, and/or a diagnosis is made to adequately explain the abnormality.

Table 6. Clinical Laboratory Tests

Hematology	
• Complete blood count with differential	
Chemistry	
• Albumin	• Creatinine clearance
• Blood urea nitrogen (BUN)	• Gamma glutamyl transferase (GGT)
• Calcium	• Glucose
• Carbon dioxide/bicarbonate	• Lactate dehydrogenase (LDH)
• Chloride	• Potassium
• Creatine kinase ^a	• Sodium
• Creatinine	• Uric acid
Liver Function Tests	
• Alkaline phosphatase (ALP)	• AST
• ALT	• Bilirubin (total and direct)
Coagulation Parameters	
• International normalized ratio (INR) time	• Prothrombin
Urinalysis	
• Bilirubin	• Proteins
• Glucose	• Red blood cells (RBCs)
• Ketones	• Screen for drugs of abuse
• Leukocytes	• Specific gravity
• Microscopy (if clinically indicated)	• Urobilinogen
• Nitrite	• Visual inspection for appearance and color
• pH	
Pregnancy Testing	
• Beta-human chorionic gonadotropin (WOCBP only)	• Urine pregnancy test
Serology	
• Hepatitis B, C, and Delta	• Human immunodeficiency virus I and II

^a Only required if ALT and/or AST is elevated 2 × higher than predose Day 1 baseline value

7.2.8. FibroScan

To exclude the presence of cirrhosis, subjects in Part B/C will have a FibroScan evaluation, unless the subject has results from a FibroScan evaluation performed within 6 months prior to screening or liver biopsy performed within 1 year prior to screening that confirm the absence of Metavir F3 fibrosis or F4 cirrhosis. If a subject has had both procedures in the specified timeframes, the most recent result should be used to determine eligibility.

8. ADVERSE EVENTS MANAGEMENT

8.1. Definitions of Adverse Events, Adverse Reactions, and Serious Adverse Events

8.1.1. Adverse Events

An adverse event is any untoward medical occurrence in a clinical study subject administered a medicinal product, which does not necessarily have a causal relationship with the treatment. An AE can therefore be any unfavorable and/or unintended sign, symptom, or disease temporally associated with the use of a medicinal product, whether or not considered related to the medicinal product. AEs may also include pre- or post-treatment complications that occur as a result of protocol specified procedures, lack of efficacy, overdose, drug abuse/misuse reports, or occupational exposure. Pre-existing conditions (recorded as medical history), which change in nature or severity should also be considered AEs.

An AE does not include the following:

- Medical or surgical procedures such as surgery, endoscopy, tooth extraction, and transfusion. The condition that led to the procedure may be an adverse event and must be reported.
- Pre-existing diseases, conditions, or laboratory abnormalities present or detected before the screening visit that do not worsen
- Situations where an untoward medical occurrence has not occurred (eg, hospitalization for elective surgery, social and/or convenience admissions)
- Overdose of study drug without clinical sequelae
- Any medical condition or clinically significant laboratory abnormality with an onset date before the consent form is signed and not related to a protocol-associated procedure is not an AE. It is considered to be pre-existing and should be documented on the medical history CRF (Case Report Form).
- Unless associated with signs or symptoms, laboratory abnormalities (eg, low platelets) should not be recorded as AEs, as these abnormalities will be captured as laboratory abnormalities
- Procedures should not be recorded as AEs; however, the condition that led to the procedure may be an AE

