Subjects enrolled in Part B/C of the study will remain outpatient. Subject screening will occur no more than 4 weeks prior to the Day 1 visit. Eligible subjects will undergo further assessments on Day 1 to qualify for study drug administration on Day 1. To exclude the presence of cirrhosis, screening will include a mandatory noninvasive assessment of liver fibrosis such as a FibroScan evaluation, unless the subject has results from a FibroScan evaluation performed within 6 months prior to screening or a liver biopsy performed within 1 year prior to screening that confirms the absence of Metavir F3 fibrosis or F4 cirrhosis.

Subjects in each cohort will be randomized 3:1 to receive VIR-2218 or placebo within 48 hours prior to study drug administration on Day 1. Subjects will return to the clinical investigative site at Week 4 to receive a second dose of the same study drug administered on Day 1. The decision to administer a second dose will be made based on Week 3 laboratory values in accordance with dose suspension/stopping criteria in Section 4.6.

CCI

Subjects will return to the clinical investigative site on an outpatient basis for safety, tolerability, PK, and antiviral activity monitoring at specified timepoints through the last Post-dose Follow-up Visit (Week 16). Additional HBsAg monitoring is required for subjects with HBsAg levels with a $> 10\%$ decrease from the Day 1 predose level at the Week 16 visit. Visits will occur

every 4 weeks starting at Week 20 up to Week 48 or until the HBsAg level returns to $\geq 90\%$ of the Day 1 predose level. Additional HBsAg monitoring may be discontinued at the Sponsor's discretion based on emerging data.

Based on review of the accumulated, available data in Parts A, B, and C, the SRC may recommend dosing of optional cohorts following the same stratification. In addition to the optional cohorts, a combined total of up to 16 "floater" subjects for Part B/C may be added to any cohort, as determined and approved by the SRC (see Section 4.5.5 and Appendix 6 for further information).

Fasting is not required for any study procedure/assessment. The assessments performed at each visit are described in Appendix 3 .

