4.4. Safety Review Committee

A SRC will perform ongoing reviews of safety, tolerability, and available study data collected throughout the study with the primary purpose of protecting the safety of subjects participating in this clinical study. The SRC will be governed by an SRC Charter that will be finalized prior to screening the first subject.

The SRC will undertake safety data review prior to initiation of dosing a new cohort in Parts A, B, and C of the study in accordance with the SRC Charter. In addition, ad hoc SRC meetings may take place as needed, eg, for a significant safety event such as a subject or cohort stopping criterion being reached (Section 4.6).

Decisions to suspend dosing or discontinue individual subjects from study drug will be made according to predetermined stopping rules (Section 4.6). Additionally, the SRC may recommend discontinuation of the study to the Sponsor. The SRC membership composition is described in detail in the SRC Charter.

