4.6.1. Cohort Stopping Rules

If any of the criteria described below are met, cohort dosing will be suspended or stopped:

- Part A only: If a sentinel subject experiences a VIR-2218-related Grade 3 or higher AE
- If 1 or more subjects experience a Grade 3 VIR-2218-related rash
- If 2 or more subjects experience the same VIR-2218-related Grade 3 or higher AE
- If 1 or more subjects experience a VIR-2218-related serious adverse event (SAE)
- If 1 or more subjects experiences a Grade 4 AE of rash, regardless of assessed causality

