4.6.2. Individual Subject Stopping Rules in Part B/C

Individual subjects in Part B/C who have received 1 dose of study drug will not receive a second dose if any the following criteria are met:

- Serum ALT > 10 × ULN
- Serum ALT > 5 × ULN, with no change (< 50% of baseline) in HBsAg
- Serum ALT or AST > 3 × ULN with a concomitant total bilirubin > 2 × ULN
- Any clinical manifestations of hepatic decompensation

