Per Section 8.1.1, laboratory abnormalities without an associated AE (signs or symptoms) and/or which do not require medical intervention, are not themselves recorded as AEs or SAEs. However, laboratory abnormalities (eg, clinical chemistry, hematology, and urinalysis) that require medical or surgical intervention must be recorded as an AE, as well as an SAE, if applicable. In addition, laboratory or other abnormal assessments (eg, electrocardiogram, vital signs) that are associated with signs and/or symptoms must be recorded as an AE or SAE if they meet the definition of an AE or SAE as described in Sections 8.1.1 and 8.1.2. If the laboratory abnormality is part of a clinical syndrome, record the syndrome or diagnosis (eg, anemia), not the laboratory result (ie, decreased hemoglobin).

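### A Grade 3 or higher non-liver laboratory abnormality that is asymptomatic and untreated is by default not an AE, so no predetermined rule holds the Part B/C Week 4 dose for it

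*Protocol*

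**What the plan says.** **Recording.** Protocol 8.1.1 says: "Unless associated with signs or symptoms, laboratory abnormalities (eg, low platelets) should not be recorded as AEs". Section 8.1.3 repeats that abnormalities without symptoms and/or without need for intervention "are not themselves recorded as AEs or SAEs". It makes exceptions for abnormalities that need medical or surgical treatment or that come with signs or symptoms. Where the abnormality is part of a syndrome, the diagnosis is recorded instead. Section 8.1.2 lets an investigator judge an important medical event to be an SAE and gives blood dyscrasias as an example.

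**Cohort rules (4.6.1).** There are five criteria:
- "Part A only: If a sentinel subject experiences a VIR-2218-related Grade 3 or higher AE"
- one related Grade 3 rash
- "If 2 or more subjects experience the same VIR-2218-related Grade 3 or higher AE"
- one related SAE
- one Grade 4 rash of any cause

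**Second dose in Part B/C.** Section 4.1.2 says the decision is "based on Week 3 laboratory values in accordance with dose suspension/stopping criteria in Section 4.6". The individual rules in 4.6.2 are ALT above 10 × ULN; "Serum ALT > 5 × ULN, with no change (< 50% of baseline) in HBsAg"; ALT or AST above 3 × ULN with bilirubin above 2 × ULN; and clinical hepatic decompensation.

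**Oversight.** Section 4.4 says: "Decisions to suspend dosing or discontinue individual subjects from study drug will be made according to predetermined stopping rules". It adds that "ad hoc SRC meetings may take place as needed, eg, for a significant safety event such as a subject or cohort stopping criterion being reached". Escalation within Part B needs SRC review of laboratory data through Week 6 (4.5.3).

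**The concern.** The protocol collects haematology, renal and coagulation results at four post-dose visits before the Week 4 dose (Day 2 and Weeks 1, 2 and 3; Appendix 3), but it states no rule for acting on a non-liver result. The recording rule takes silent abnormalities out of the AE count, and the stopping rules count only AEs, SAEs and rash. Low platelets, the recording rule's own example, shows the consequence: two of the three active subjects in a cohort could have a related, asymptomatic Grade 3 fall by Week 3 without meeting a stated criterion.

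What is at stake is control of dosing within a cohort while it is running. Whether either subject, or the cohort, receives the Week 4 dose would depend on someone choosing to act.

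**Working it through.** The plan gives no figure to reproduce: Protocol 9.8 reports no formal sample size calculation, and no operating characteristics are given for the stopping rules. The main check is of the text. The arithmetic is illustration.

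**Step 1. Rules against the recording default.** Take a Grade 3+ platelet, neutrophil or creatinine value that is asymptomatic, untreated, not part of a syndrome and not judged an important medical event.
- 4.6.1: 0 of 5 criteria are met, because each needs an AE, SAE or rash.
- 4.6.2: 0 of 4 criteria concern a non-liver parameter.
- 4.1.2 sends the Week 3 laboratory check only to Section 4.6, so that check adds nothing for such a value.
- Causality is assessed for AEs and SAEs (8.2, 8.2.1), so relatedness of such a value need not be recorded.

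**Step 2. Timing.** The second dose is at Week 4. The mandatory SRC laboratory review for the ongoing cohort uses Week 6 data (4.5.3). It protects the next cohort, not this dose.

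**Step 3. Illustration of size.** A Part B/C cohort has 4 subjects randomized 3:1, so n = 3 active. Let p be the assumed proportion of active subjects with the same related, confirmed, countable Grade 3+ laboratory abnormality, and let half of these be silent and untreated. The documents give neither value; p from 5% to 30% is an assumption.

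- Two-subject rule: P(X ≥ 2) = 3p² − 2p³. The amended rule uses p; the rule as written uses p/2.
- One-subject criterion, silent share only, q = p/2: P(at least one of 3) = 1 − (1 − q)³.

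| p | Two-subject, as written | Two-subject, amended | Gain | At least one silent case |
|---|---|---|---|---|
| 0.05 | 0.0018 | 0.0073 | 0.0054 | 0.073 |
| 0.10 | 0.0073 | 0.0280 | 0.0208 | 0.143 |
| 0.20 | 0.0280 | 0.1040 | 0.0760 | 0.271 |
| 0.30 | 0.0608 | 0.2160 | 0.1552 | 0.386 |

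Example at p = 0.30: amended 3(0.09) − 2(0.027) = 0.216; as written 3(0.0225) − 2(0.003375) = 0.0608.

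If the silent share is 25%, the gain is 0.3 to 8.7 percentage points; if 100%, it is 0.7 to 21.6. Over the four planned Part B/C cohorts, the 50% case gives 4 × 0.0054 = 0.02 to 4 × 0.1552 = 0.62 extra two-subject triggers. Among the 4 × 3 = 12 active subjects, it gives 12 × 0.025 = 0.3 to 12 × 0.15 = 1.8 silent cases.

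These figures overstate the effect on dosing. They ignore whether events appear before Week 4, and the as-written column leaves out the syndrome and important-medical-event routes.

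**Step 4. Time to confirm a Week 3 value.** Week 3 is Day 22 ± 2 and Week 4 is Day 29 ± 2. The gap is nominally 29 − 22 = 7 days, at least 27 − 24 = 3 and at most 31 − 20 = 11, so most repeat samples should fit.

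**The case against.** The strongest case is that judgment already covers this. Section 8.1.2 offers blood dyscrasias as a possible SAE, and one related SAE suspends a cohort; for platelets and neutrophils that route can act on a single subject. Section 8.1.3 has the diagnosis recorded when a value belongs to a syndrome. Section 4.3 provides for subjects discontinued for reasons other than an AE. The Sponsor reviews safety on an ongoing basis (1.3), ad hoc SRC meetings may be called (4.4), and relevant abnormal tests are repeated (7.2.7). Part A Week 4 data at the same or a higher cumulative dose must be reviewed first (4.5.3). Liver-focused rules also suit a drug that goes mainly to the liver (1.2.4), and the available text shows no platelet, neutrophil or renal signal.

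Much of this stands, and it rules out three stronger readings that a reader might infer:
- *Laboratory abnormalities can never meet a stopping rule.* Sections 8.1.2 and 8.1.3 leave routes open.
- *Section 4.6 is the only basis for stopping a subject.* The sentence in 4.4 suggests it, but 4.3 shows otherwise.
- *The safety analysis will miss these events.* Laboratory results are a primary endpoint, and SAP 12.2.1 tabulates maximum CTCAE grade using scheduled and unscheduled visits.

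What remains is that the important-medical-event, ad hoc and follow-up routes are discretionary, while 8.1.1 tells sites not to record these values as AEs. Part A evidence comes from a single dose in healthy adults up to 55 with creatinine clearance of at least 90 mL/min; Part B/C admits patients up to 65 with clearance down to 60 mL/min. The SRC Charter was not available and may add criteria, but that would not change what Section 4.6 says.

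**Conclusion.** The point holds as a gap in predetermined, within-cohort dosing rules in Part B/C. By default, a silent, untreated Grade 3+ non-liver abnormality triggers no cohort rule, and no stated rule holds the Week 4 dose of the subject or the cohort.

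Its reach is limited. Escalation is already gated by SRC laboratory review, and the final analysis is unaffected. The gain of 0.5 to 15.5 percentage points per cohort is illustrative only: it rests on unsourced rates, and 30% sharing one related Grade 3+ abnormality would be extreme given the laboratory entry criteria. An extended two-subject rule would fire rarely. On its own it would also leave one subject with a confirmed abnormality open to redosing, so an individual criterion is needed.

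The Part A sentinel step is a minor side issue. The items listed for review in 4.1.1 omit laboratory results although Day 2 samples are scheduled, and only one sentinel is active before six more subjects (five active) are dosed. But dosing proceeds only if the investigator has no safety concerns, and nothing bars looking at laboratory results. No size is claimed there.

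**What to change.** 1. **4.6.2:** add that a Part B/C subject with a confirmed, VIR-2218-related CTCAE Grade 3 or higher non-liver laboratory abnormality has the second dose withheld pending SRC review. Define confirmed as Grade 3 or higher again on a repeat sample. Repeat a Week 3 value before the Week 4 dose, and allow a short delay past Day 31 if the result is late.
2. **4.6.1:** extend the two-subject rule to the same related Grade 3 or higher AE or confirmed Grade 3 or higher laboratory abnormality, whether or not recorded as an AE, leading to suspension pending ad hoc SRC review. Have the investigator record relatedness for such values. In Part B/C, count ALT and AST only when a 4.6.2 criterion is met, which keeps the HBsAg-conditional rule intact.
3. **Optional and minor:** extend the Part A sentinel rule in the same way and add available Day 2 laboratory results to the sentinel review.

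The cost is protocol wording and one relatedness field; CTCAE grading is already planned (Protocol 9.5.2, SAP 12.2.1). The downside is occasional ad hoc SRC meetings, short delays of some Week 4 doses and, if item 3 is adopted, a short wait for Day 2 results.
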